4.2. Objectives

4.2.1. Primary Objective(s)

- Stimulated (90 minute sample of a MMTT) C-peptide at the 1 year visit greater or equal to baseline level.

4.2.2. Secondary Objective(s)

- Stimulated C-peptide area under the curve (AUC) during a 4-hour MMTT greater or equal to baseline level, at the 1 year visit.
- Reduction in HbA1c at the one year visit compared to baseline.
- Reduction in insulin requirement at the 1 year visit compared to baseline.
- Incidence of adverse events (AE) comparable to general diabetes population.

4.3. Investigational Plan

This is a randomized, open-label, parallel-group, pilot phase I/IIa clinical study. Approximately 56 subjects will be randomly assigned to receive either Omega-3 Fatty Acids and Vitamin D combination or Vitamin D alone. All subjects will be given Vitamin D supplement. Patients to be included in this study are those diagnosed with new onset T1D (diagnosed within the last 180 days) or with established T1D (more than 6 months).

Participation for each subject will last approximately 2 years. Potential participants will have a screening visit to review their overall health, measure diabetes T1D-associated autoantibodies and perform a MMTT, which will also serve as the baseline MMTT. Eligible subjects will be invited to participate in the intervention trial for one year, and then followed for a second year to monitor safety and whether any potential therapeutic benefit, whether metabolic, endocrine, and/or immunological, persists after the therapy has been stopped.

We will evaluate beta cell function by examining C-peptide responses during a MMTT.

4.4. Summary of Inclusion and Exclusion Criteria

This study can fulfill its objectives only if appropriate patients are enrolled. The following eligibility criteria are designed to select patients for whom protocol treatment is considered appropriate. All relevant medical and non-medical conditions will be taken into consideration when deciding whether this protocol is suitable for a particular participant.

We will enroll T1D patients of both genders, 6-65 years -old, to examine the Omega-3 Fatty Acids and Vitamin D supplements covering as much of the age spectrum of the disease in both established as well as new onset T1D patients. There will be no restriction on race and ethnicity. However, T1D is more prevalent in populations of European descent, and enrollment will likely reflect disease prevalence in the Miami area, where the population is diverse and enriched in ethnicities from Latin America. Subjects who fulfill the following eligibility criteria will be recruited regardless of their race or gender.

4.4.1. Inclusion Criteria

Patients **must meet all** of the following criteria to be eligible to participate in this study:

1. Subjects or their parents if under 18 years old must be able to understand and provide informed consent.
2. Males and females, 6-65 years of age.
3. For new onset T1D subjects, ≤ 180 days from T1D diagnosis at the time of randomization with a MMTT stimulated C-peptide peak level ≥ 0.2 ng/ml prior to randomization.
4. For established T1D subjects, > 180 days and ≤ 10 years of T1D duration at the time of randomization and MMTT stimulated C-peptide peak level ≥ 0.2 ng/ml prior to randomization.
5. Affected by T1D, according to ADA standard criteria, and confirmed by positivity of at least one T1D-associated autoantibody, to GAD65, IA-2, ZnT8, or insulin autoantibodies (if patient has been treated with insulin for less than 2 weeks).
6. Female subjects of childbearing potential must have a negative pregnancy test upon study entry.
7. Adequate venous access to support study required blood draws.
8. T1D must be treated with insulin (except if participant is in Honeymoon period/phase).

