Females of child bearing potential must have a negative pregnancy test prior to enrolling in the study and will be required to use at least two FDA approved birth control during the study. At every study visit the sexual activity of female participants of reproductive age will be re-assessed. Pregnancy testing will be conducted in females in reproductive age at 4, 8, 12 and 16 months study visit. If a subject who was previously sexually inactive becomes sexually active, she will be counseled about the need to use a reliable forms of birth control. Subjects will be requested to avoid pregnancy for 6 months following the last study administration and instructed to use birth control. If subject becomes pregnant, study intervention will be discontinued and subject withdrawn from study.

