6.3. Screening (visit 0) and Baseline (visit 1) visits

Patients will be asked to sign consent for screening to determine eligibility. Patients will receive a physical exam, medical history will be taken, and basic physical parameters will be recorded (height, body weight, heart rate, blood pressure). Blood will be drawn for laboratory assessments (see section 6.5) for evaluation of inclusion and exclusion criteria.

A patient that meets the inclusion/exclusion entry criteria will be randomized to one of the two treatment arms. Blood will be drawn for baseline visit (visit1) assessments. The patient will receive the first treatment dose within 48 hr from the baseline visit.

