6.8. Visit Windows

The initial study drug administration must begin within 180 days from the day of diagnosis. All subsequent treatment visits and follow up visits in Appendix 1 must occur within the time limits specified below:

The table below depicts summary of visit windows.

Visit Windows	
Visit 0	At least 2 weeks before visit 1
Visit 1	New onset group (randomization \leq 180 days from T1D diagnosis) or established T1D ($>$ 180 days and $<$ 10 years from T1D diagnosis)
Visit 2-4 (Days 120, 240, 360)	\pm 14 days
Follow-up between year 1 and 2	
Every four months	\pm 14 days

During the course of the study, participants who complete one year treatment will receive combination therapy of Omega-3 Fatty Acids and Vitamin D or Vitamin D alone. In addition, participants will frequently undergo assessments of their insulin production, immunological status, and overall health. The participant's insulin production will be measured by a series of MMTTs conducted regularly during the study. The participant's diabetes control will be evaluated by measuring HbA1c every four months and clinical records including insulin types, doses, administration times and blood glucose records.

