6.18. Pregnancy

Pregnant and lactating women will not be included in the study. Sexually active females must have a negative pregnancy test prior to enrolling in the study and will be required to use at least two FDA approved birth control during the study. At every study visit the sexual activity of female participants of reproductive age will be re-assessed. If a subject who was previously sexually inactive becomes sexually active, she will be counseled about the need to use a reliable forms of birth control. Subjects will be requested to avoid pregnancy for 6 months following the last study administration and instructed to use birth control.

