APPENDIX A: Schedule of Events (SOE)

Visit number	0	1	2	3	4	5 F1	6 F2	7 F3
Days of the trial ¹	-1	1	120	240	360	480	600	720
Months	1	1	4	8	12	16	20	24
Informed Consent	X							
Medical History	X		X	X	X	X	X	X
Physical Exam ²	X		X	X	X	X	X	X
CBC with differential	X	X	X	X	X			
Prothrombin time (PT/PT-INR)	X		X	X	X	X	X	X
Chemistries	X		X	X	X			
Pregnancy test (blood sample) ⁵	X		X	X	X			
Serum for islet autoantibodies	X		X	X	X	X	X	X
Serology	X							
Mechanistic assessments ³		X	X	X	X	X	X	X
Hemoglobin A1c	X		X	X	X	X	X	X
Stimulated C-peptide at 90 min	X				X			X
MMTT 4 hour	X				X			X
Randomization			X					
Diabetes Assessments (insulin adjustment and Hypoglycemia awareness)	X	X	X	X	X	X	X	X
Clarke Score	X				X			X
Dispensing or Administration of Study Drug		X ⁶	X	X				
• Omega-3 Fatty Acids + Vitamin-D OR • Vitamin-D								
Vitamin D levels ⁴	X		X	X	X	X	X	X
AA/EPA Ratio ⁷	X		X	X	X	X	X	X
Counting of Returned Study Drug			X	X	X			
Subject 7-day blood sugar record and hypoglycemia log	X		X	X	X	X	X	X
Concomitant Medication Review	X	X	X	X	X			
Adverse Events Assessment			X	X	X	X	X	X

1. Screening Visit: Screening MMTT must be at least 3 weeks after diagnosis and preferably within one month (37 days) of randomization for recent onset T1D. For established T1D, screening must take place after 180 days of diagnosis.
2. Physical Exam: Routine exam at screening and quarterly.

3. Mechanistic Assessments: includes samples for RNA, plasma, serum, DNA, measures of B and T cell number/function and cytokine profiles. The schedule for these assessments may vary as appropriate. At no time will the blood draw volume exceed what is allowable according to the subject's body weight.
4. Vitamin D levels will be monitored every 4 months or more frequently at the discretion of the investigator in order to adjust dose to achieve target levels.
5. Pregnancy testing will be conducted in females in reproductive age at 4, 8,12 and 16 months study visit.
6. Study drug(s) will be administered within 48hr from baseline visit (visit 1).
7. Dose will be adjusted to maintain a target AA/EPA ratio of 1.5-3.0. AA/EPA ratios will be monitored monthly until achieving target levels and as per protocol or as clinically indicated thereafter.

F1-F3. Follow-Up after 12 Months: Visits will be conducted approximately every 4 months (16, 20, and 24 months).

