APPENDIX B: Blood Sample Collection Amounts by Age Group and Weight

➤ Ages ≥ 18 y/o (Adults)

Maximum Draw Allowed Per 8 Week Period: 10.5 mL/kg or 550 mL

Visit number	0	1	2	3	4	5 F1	6 F2	7 F3
Days of the trial	-1	1	120	240	360	480	600	720
Months	1	1	4	8	12	16	20	24
CBC with differential	2 mL	2 mL	2 mL	2 mL	2 mL			
Prothrombin time (PT/PT-INR)	1.8 mL		1.8 mL					
Chemistries	3.5 mL		3.5 mL	3.5 mL	3.5 mL			
Pregnancy test ¥	¥		¥	¥	¥	3.5 mL		
Serum for islet autoantibodies	3.5 mL		3.5 mL					
Serology	3.5 mL							
Mechanistic assessments §		21 mL	21 mL	21 mL	21 mL	21 mL	21 mL	21 mL
Hemoglobin A1c	2 mL		2 mL					
Simulated C-peptide at 90 min*	X				X			X
MMTT 4 hour	38.5 mL				38.5 mL			
Vitamin D levels	3.5 mL		3.5 mL					
AA/EPA Ratio	2 mL		2 mL					
Total Blood collection per visit	60.3 mL	23 mL	39.3 mL	39.3 mL	77.8 mL	37.3 mL	33.8 mL	33.8 mL

¥ Pregnancy test for visits -1; 120; 240, and 360 will be performed using same serum sample for chemistry. For visit 480 a 3.5 mL SST tube (serum sample) will be collected to perform the test in the absence of a chemistry sample requirement

§ Mechanistic Assessments: includes samples for RNA, plasma, serum, DNA, measures of B and T cell number/function and cytokine profiles. The schedule for these assessments may vary as appropriate. At no time will the blood draw volume exceed what is allowable according to the subject's body weight.

Mechanistic Samples (total volume: 21 ml) as follows:

Pro-inflammatory cytokines: 3.5 mL

Phenotyping: 2 mL

RNA: 2.5 mL

DNA: 2.5 mL

Resolvin: 2 mL

LPS activation T-cell stimulation assay: 3 mL

Plasma: 2 mL

Serum: 3.5 mL

*Stimulated c-peptide at 90 min is a time point of the MMTT. No extra sample collection needed.

- Ages 6 to <18 y/o
- Weight at screening visit (Kg): 27 and greater

Maximum Draw Allowed Per Day (5mL/Kg): 135 mL/kg

Maximum Draw Allowed Per 8 Week Period (9.5 mL/Kg): 257 mL

Visit number	0	1	2	3	4	5 F1	6 F2	7 F3
Days of the trial	-1	1	120	240	360	480	600	720
Months	1	1	4	8	12	16	20	24
CBC with differential	2 mL	2 mL	2 mL	2 mL	2 mL			
Prothrombin time (PT/PT-INR)	1.8 mL		1.8 mL					
Chemistries	3.5 mL		3.5 mL	3.5 mL	3.5 mL			
Pregnancy test ¥	¥		¥	¥	¥	3.5 mL		
Serum for islet autoantibodies	3.5 mL		3.5 mL					
Serology	3.5 mL							
Mechanistic assessments §		21 mL	21 mL	21 mL	21 mL	21 mL	21 mL	21 mL
Hemoglobin A1c	2 mL		2 mL					
Simulated C-peptide at 90 min*	X				X			X
MMTT 4 hour	38.5 mL				38.5 mL			
Vitamin D levels	3.5 mL		3.5 mL					

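### The only scheduled pregnancy test before dosing is at visit 0, and the protocol does not fix how long before the first dose that test may be

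*Combined protocol and SAP*

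**What the plan says.** **The requirement.** Section 4.4.1, criterion 6: "Female subjects of childbearing potential must have a negative pregnancy test upon study entry". Section 5.4.8 words it as "Females of child bearing potential must have a negative pregnancy test prior to enrolling in the study". Section 6.18 has a different population: "Sexually active females must have a negative pregnancy test prior to enrolling in the study". None of these gives an interval between test and first dose. Pregnancy is an exclusion (section 4.4.2, criterion 22) and a reason to stop study drug (sections 5.4.6, 5.4.8 and 7.1.11).

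**The schedule.** In Appendix A the pregnancy row is marked at visits 0, 2, 3 and 4 and is blank at visit 1. Appendix B says the same in words: "Pregnancy test for visits -1; 120; 240, and 360 will be performed using same serum sample for chemistry", with a separate tube at day 480. Footnote 5 of Appendix A gives the on-study tests: "Pregnancy testing will be conducted in females in reproductive age at 4, 8,12 and 16 months study visit".

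**The timing.** Section 6.8 places visit 0 "At least 2 weeks before visit 1", whereas the headers of Appendices A and B put it at day -1. Footnote 1 of Appendix A wants the screening MMTT "preferably within one month (37 days) of randomization for recent onset T1D". Section 6.3: "The patient will receive the first treatment dose within 48 hr from the baseline visit".

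**The concern.** A criterion that calls for a negative test at entry is meant to keep pregnant participants off study drug. As scheduled, the result that satisfies it can predate the first dose by weeks, and nothing at visit 1 updates it. A participant who conceives after screening meets an exclusion criterion by the time she is dosed, yet no scheduled test would show this before dosing. Both arms receive study drug, so the matter is not confined to the omega-3 arm.

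The sections also disagree on when visit 0 falls and on who must be tested. A site could follow the protocol in good faith and still apply the criterion differently from one participant to the next.

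**Working it through.** There is no stated figure to reproduce. The check is a comparison of sections with date arithmetic.

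**1. Tests against dosing**

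| Visit | Day | Scheduled pregnancy test | Study drug |
|---|---|---|---|
| 0 | -1 (appendix headers), or at least 14 days before visit 1 (6.8) | Yes | None |
| 1 | 1 | None | First supply; first dose within 48 h |
| 2 | 120 ± 14 | Yes | Dispensed |
| 3 | 240 ± 14 | Yes | Dispensed |
| 4 | 360 ± 14 | Yes | None dispensed |
| 5 | 480 ± 14 | Footnote 5 and Appendix B: yes; Appendix A row: no mark | None |

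**2. Is the blank at visit 1 only a lost table entry?** The blood volumes in Appendix B can be summed.
- Visit 1: 2 (CBC) + 21 (mechanistic) = 23 mL, the stated total. There is no pregnancy tube, and no chemistry tube from which a test could be run.
- Visit 0: 2 + 1.8 + 3.5 + 3.5 + 3.5 + 2 + 38.5 + 3.5 + 2 = 60.3 mL, as stated.
- Visit 2: 2 + 1.8 + 3.5 + 3.5 + 21 + 2 + 3.5 + 2 = 39.3 mL, as stated.
- Visit 5: 1.8 + 3.5 + 3.5 + 21 + 2 + 3.5 + 2 = 37.3 mL, as stated, including the 3.5 mL pregnancy tube.

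The totals agree with the Appendix B footnote, so the blank at visit 1 is what the plan intends.

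**3. Age of the last scheduled test at the first dose** (first dose 0 to 2 days after visit 1)
- Minimum under section 6.8: 14 + 0 to 14 + 2 = 14 to 16 days.
- At the preferred limit for new onset: 37 + 0 to 37 + 2 = 37 to 39 days. This is a preference, and it is written for the screening MMTT.
- Outer bound for new onset: the screening MMTT is at least 3 weeks after diagnosis and randomization is by day 180, so 180 - 21 = 159 days. This takes the pregnancy test to be at the same visit as the MMTT.
- Established disease: no maximum found.
- If the day -1 header is right: about 1 to 2 days before visit 1.

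**4. Time to the next scheduled test.** Visit 2 may fall from day 120 - 14 = 106 to day 120 + 14 = 134, which is 105 to 133 days after day 1.
- With a 14-day screening interval, the gap between scheduled tests is 14 + 105 = 119 to 14 + 133 = 147 days.
- With a 37-day interval it is 37 + 105 = 142 to 37 + 133 = 170 days.
- Dosing before that test can last 106 - 3 = 103 to 134 - 1 = 133 days.

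**5. Who is tested.** Sections 4.4.1 and 5.4.8 refer to childbearing potential, section 6.18 to sexual activity, and footnote 5 to reproductive age. These groups are not the same.

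**The case against.** The strongest reply is that nothing is contradicted. Sections 5.4.8 and 6.18 ask for the test before enrolling, and section 6.3 draws screening blood to judge eligibility. A visit 0 result therefore satisfies the criterion as the protocol uses it. This stands: because entry is undefined, a reader might infer a flat contradiction between criterion 6 and the schedule, and the text does not support one. What remains is that no section says how old a qualifying result may be at the first dose.

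The 14-day figure rests on section 6.8 alone, and the appendix headers point to a test only a day or two old. That also stands. It narrows the gap if the header is right, but the two must then be reconciled, and visit 1 has no test on either reading.

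The protocol also has safeguards. It requires two contraceptive methods, excludes those unwilling to use contraception, re-assesses sexual activity at every visit, and allows testing where appropriate (section 6.5). Section 7.1.11 covers a pregnancy discovered after exposure. These lower the probability and could reveal a pregnancy earlier. None is a scheduled test before dosing.

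Three further inferences should be resisted.
- The 103 to 133 days of possible dosing are not all due to the missing test. Tests are four months apart throughout treatment, so a conception just after visit 1 would wait equally long. A test at visit 1 could also miss a very early pregnancy.
- The upper-intake table in section 5.4.2.1 does not give a pregnancy-specific excess for the weekly vitamin D course: it lists 4,000 IU for everyone aged 9 or over and the same for pregnancy. A count of weekly doses is not firm either, since section 1.1 gives 6 months and section 5.4.2.1 gives 4 months for levels below 20 ng/ml.
- The 3.5 mL of serum drawn at visit 1 is a mechanistic sample and cannot be assumed free for a pregnancy test.

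**Conclusion.** The point holds as a gap between the entry criterion and the schedule. Under section 6.8, the last scheduled test is at least 14 days before visit 1, with no firm stated maximum. New onset is bounded indirectly at about 159 days and established disease is not bounded. A conception in that interval would not be found by a scheduled test before dosing; the next scheduled test falls between days 106 and 134. As written, the plan can therefore dose a participant who meets exclusion criterion 22.

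The size depends on which statement of visit 0 is right. If it is day -1, the unprotected interval shrinks to a few days. The documents give no pregnancy rate, so no expected number of affected participants can be stated; with the contraception requirement the probability should be low. A correction is still warranted, because the matter concerns participant safety and costs little to settle.

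**What to change.** Reconcile sections 4.4.1, 5.4.8, 6.3, 6.8 and 6.18 with Appendices A and B. The clinical rule is for the sponsor to decide; the protocol then needs to state it once and schedule it.

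- State which pregnancy test qualifies a participant and when it must fall relative to the first dose, and make both appendices deliver it.
- Resolve the day -1 header against the 2-week minimum in section 6.8.
- Use one definition of who is tested in sections 4.4.1, 5.4.8 and 6.18.
- Mark the month-16 test in the Appendix A row, to match footnote 5 and Appendix B.

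**Cost.** At most one additional test per female of childbearing potential, possibly with a dedicated 3.5 mL tube like the one at day 480. If such a tube were drawn at visit 1, that visit would total 23 + 3.5 = 26.5 mL, and visits 0 and 1 together 60.3 + 26.5 = 86.8 mL. In the lightest pediatric band (from 16 kg) the limits are 5 mL/kg × 16 kg = 80 mL per day and 152 mL per 8 weeks, so the volume fits when the two visits are on separate days. The documents give no turnaround time for the result, so the sponsor would need to confirm that it fits the 48-hour dosing window.

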4.4.2. Exclusion Criteria

Potential participants **must not** meet any of the following exclusion criteria:

1. Inability or unwillingness of a participant or their parents to give written informed consent or comply with study protocol.
2. $BMI > 30$ Kg/m².

3. Contra-indications to Omega-3 Fatty Acids and/or Vitamin-D (e.g., knowledge of hypersensitivity to drugs or its excipients, allergies with fish or shellfish etc.).
4. Uncompensated heart failure, fluid overload, myocardial infarction or liver disease or severe impairment of a vital organ within the last 6 weeks before enrollment.
5. Any sign or diagnosis of significant chronic active infection (e.g., hepatitis, tuberculosis, EBV, or CMV), or screening laboratory evidence consistent with a significant chronic active infection (such as positive for HIV, IGRA test for TB, or hepatitis B-C).
6. Ongoing acute infections, e.g., acute respiratory tract urinary tract, or gastrointestinal tract infections.
7. Subjects on weight altering medications, such as Orlistat.
8. Subjects with eating disorders
9. Ongoing or anticipated use of diabetes medications other than insulin.
10. Current or ongoing use of non-insulin pharmaceuticals that affect glycemic control within prior 7 days of screening.
11. People who chronically take drugs that affect bleeding time, such as anticoagulants ("blood thinners") or nonsteroidal anti-inflammatory drugs (NSAIDs), will not qualify to enroll in the study.
12. Recent recipient of any licensed or investigational live attenuated vaccine(s) within 6 weeks of randomization.
13. Use of investigational drugs within 4 months of participation.
14. Concomitant therapy with immunosuppressive drugs, immunomodulators, or cytotoxic agents, or previous therapy less than 3 months from randomization.
15. History or diagnosis of malignancy.
16. History of gastroparesis or other severe gastrointestinal disease.
17. History or diagnosis of malignancy with the exception of a history of localized basal or squamous cell carcinoma. There is conflicting evidence about whether omega-3 fatty acids found in seafood and fish oil might increase the risk of prostate cancer. Until additional research on the association of omega-3 consumption and prostate cancer risk is conducted, subjects with family history of prostate cancer in a first-degree relative will be excluded from the study.
18. Presence of an allograft.
19. AST, ALT or Alkaline Phosphatase >2 times upper limit of normal or total bilirubin >1.5 times upper limit of normal.
20. History of a mental illness deemed to be clinically unstable or any situation that, in the opinion of the investigator, would interfere with the participant's ability to comply with study requirements.

21. History of illicit drug or alcohol abuse.
22. Pregnancy or ongoing breastfeeding for women; unwillingness or inability of both females and males of childbearing age to use a reliable and effective form of contraception, for the entire duration of the study.
23. Past or current medical problems, or findings from physical examination, or laboratory testing, that are not listed above which, in the opinion of the investigator, may pose additional risks from participation in the study, may interfere with the participant's ability to comply with study requirements or that may impact the quality or interpretation of the data obtained.
24. All patients who have coagulation, bleeding, or blood disorders will be excluded due to the effect of high dose of Omega 3 Fatty Acids on coagulation and bleeding process.

